### **4.6.1 Early Termination Study Visit**

Subjects who withdraw from the study will have all procedures enumerated for Visit 5 as the early termination visit if at least 4 weeks have elapsed since the start of the 12-week intervention.

---

## 5 STUDY EVALUATIONS AND MEASUREMENTS

### 5.1 Screening and Monitoring Evaluations and Measurements

#### 5.1.1 Medical Record Review

Participants will be interviewed regarding their medical history. To ensure that no major items are missed and to clarify interview answers, the study team will review participant electronic medical records prior to and after the participant interview to confirm the following:

- Date of birth
- Birth history (gestational age, birth weight, complications during pregnancy)
- Anthropometrics (weight, height, BMI)
- Medications
- List of medical problems, especially as they relate to inclusion and exclusion criteria
- Demographic data including race, ethnicity, gender, and insurance type
- Endocrine-related diagnoses, including: insulin resistance, prediabetes, impaired glucose tolerance, impaired fasting glucose, elevated hemoglobin A1c, diabetes mellitus, and polycystic ovary syndrome
- History of attendance at an obesity clinic
- History of bariatric surgery
- Diabetes-related labs, including: plasma and point-of-care glucose, hemoglobin A1c, and insulin
- History of non-alcoholic fatty liver disease, non-alcoholic steatohepatitis, elevated ALT or AST, or other known liver disease

#### 5.1.2 Physical Examination

A study physician (pediatric endocrinologist) will review with the parent and child the child's current and past medical history, a review of systems, and family history (with particular attention to cardiovascular disease and diabetes). A focused physical examination will be conducted, including measurement of height, weight, waist circumference, hip circumference, pubertal staging, and pertinent physical findings associated with insulin resistance, including the presence of acanthosis nigricans, which will be recorded on a standardized form. Investigators will verify that the patient has been fasting for a minimum of 12 hours.

---

### 5.1.3 Vital Signs

- Blood pressure (BP) will be recorded while the subject is sitting down by the nursing staff. BP will be measured by auscultation three times, after a five minute rest in a quiet area with the subject in a seated position; the average of the 2nd and 3rd measurements will be used.
- Pulse and respiratory rate will be measured by nursing staff

### 5.1.4 Laboratory Evaluations

#### 5.1.4.1 *Table: Clinical Laboratory Tests*

Category	Tests
Biomarkers of glucose metabolism	Hemoglobin A1c, plasma glucose, insulin
Liver function tests	SGOT/AST, SGPT/ALT
Lipids	Triglycerides, LDL, HDL

#### 5.1.4.2 Pregnancy Testing

A urine pregnancy test will be performed for all female subjects at baseline. A positive pregnancy result will be disclosed to the participant only. Pregnancy results will be disclosed to the parent/guardian if the subject gives the investigators permission. Subjects found to be pregnant during the visit will not be able to enroll in this study. The investigators will counsel the subject and guide them to seek the appropriate care.

### 5.1.5 Medical History and Family History Questionnaire

Will include past medical history, 1st and 2nd degree family history of diabetes, dyslipidemia, cardiovascular disease, and socioeconomic status questions.

### 5.1.6 Dietary Recalls

During weeks 1-2 of the intervention, three 24-hour (2 weekday, 1 weekend) dietary recall interviews of participants will be conducted by a Children's Hospital of Pittsburgh registered dietitian via phone or in-person. Reported intake will be entered into a nutrition application (e.g. CalorieKing), without any patient-identifying information, in order to determine nutrition information including calories, protein, saturated fat, fatty acids, added sugar, and sodium. These data will be used to calculate the Healthy Eating Index score, (Krebs-Smith, Pannucci et al. 2018) using the scoring standards listed in **Figure 3**.

**HEI-2015 Components and Scoring Standards**

Component	Maximum points	Standard for maximum score	Standard for minimum score of zero
Adequacy:			
Total Fruits 	5	≥0.8 cup equivalent per 1,000 kcal	No Fruit
Whole Fruits 	5	≥0.4 cup equivalent per 1,000 kcal	No Whole Fruit
Total Vegetables 	5	≥1.1 cup equivalent per 1,000 kcal	No Vegetables
Greens and Beans 	5	≥0.2 cup equivalent per 1,000 kcal	No Dark-Green Vegetables or Legumes
Whole Grains	10	≥1.5 ounce equivalent per 1,000 kcal	No Whole Grains
Dairy 	10	≥1.3 cup equivalent per 1,000 kcal	No Dairy
Total Protein Foods 	5	≥2.5 ounce equivalent per 1,000 kcal	No Protein Foods
Seafood and Plant Proteins 	5	≥0.8 ounce equivalent per 1,000 kcal	No Seafood or Plant Proteins
Fatty Acids 	10	(PUFAs + MUFAs) / SFAs ≥2.5	(PUFAs + MUFAs)/SFAs ≤1.2
Moderation:			
Refined Grains	10	≤1.8 ounce equivalent per 1,000 kcal	≥4.3 ounce equivalent per 1,000 kcal
Sodium	10	≤1.1 grams per 1,000 kcal	≥2.0 grams per 1,000 kcal
Added Sugars	10	≤6.5% of energy	≥26% of energy
Saturated Fats	10	≤8% of energy	≥16% of energy

 Intakes between the minimum and maximum standards are scored proportionately.

 Includes 100% fruit juice.

 Includes all forms except juice.

 Includes legumes (beans and peas).

 Includes all milk products, such as fluid milk, yogurt, and cheese, and fortified soy beverages.

 Includes seafood; nuts, seeds, soy products (other than beverages), and legumes (beans and peas).

 Ratio of poly- and mono-unsaturated fatty acids (PUFAs and MUFAs) to saturated fatty acids (SFAs).

**Figure 3.** Healthy Eating Index-2015 Components and Score Standards;  
<https://www.fns.usda.gov/how-hei-scored>.

### 5.1.7 Questionnaire Assessment

**PACE+ adolescent physical activity questionnaire** will be administered by the study coordinator or appropriate member of the investigative team. PACE+ is a validated, two question measure of physical activity.(Prochaska 2000)

**Monetary Choice Questionnaire (MCQ)** is a set of 27 questions developed by Kirby et al(Kirby, Petry et al. 1999) that is used to measure temporal discounting, or the tendency to prefer smaller, sooner rewards over larger, delayed rewards. It is a self-administered questionnaire that has been used in numerous studies of adults and adolescents. Ten ranges of discount rates are used, with delays ranging from 7-186 days. To evaluate the degree of delay discounting, a hyperbolic function is fit to bivariate data on indifference points between delayed rewards (small, medium, and large rewards) and delay. A parameter (k) resulting from the model may be used to compare discount tendencies across individuals or over time.

**Behavioral Regulation in Exercise Questionnaire-3 (BREQ-3)** is a 24-item questionnaire drawing from Self-Determination Theory(Ryan and Deci 2000) that asks respondents to rate statements about physical activity behaviors as “Not true for me,” “Sometimes true for me,” or “Very true for me.”(Mullan, Markland et al. 1997, Wilson, Rodgers et al. 2006) It is used to assess motivation on the spectrum of intrinsic to extrinsic to amotivation and has been

[figure not shown]
used to assess motivation to perform physical activity in adolescents.(Navarro, Escobar et al. 2020)

### 5.1.8 Exit Interview

Semi-structured individual interviews will be conducted by study staff in a private setting at visit 5 to evaluate intervention acceptability, including constructs of burden, perceived effectiveness, and impact on physical activity-related self-efficacy. Interviews will be audiorecorded and then transcribed by a University of Pittsburgh-approved vendor.

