Study Phases	
Screening and recruitment: Potential subjects will be identified via review of Endocrinology clinic schedules weekly and by using the CAYAH RESEARCH INTEREST FORM distributed by Adolescent medicine. After potential subjects are identified, they will be contacted along with their parents/guardians (as applicable), to screen for eligibility. Subjects will be consented and will be scheduled for a morning study visit at the Pediatric Clinical and Translational Research Center (PCTRC). They will be instructed to complete an overnight 12 hour fast at home prior to the study visit.
 
Visit 1 (in-person): Participants will undergo fasting laboratory evaluations, vitals, anthropometry, pubertal status, medical history, and physical activity and behavioral questionnaires. Participants will be given Fitbit physical activity trackers to wear for the duration of the study during waking hours and will be instructed on use.
 
Run-In: Participants will wear the Fitbit daily during waking hours for 14 consecutive days. They will receive daily reminder text messages to wear the Fitbit. At the end of 14 days, mean daily MVPA and number of days Fitbit was worn during days 8-14 will be determined. Participants will be excluded if their MVPA was >30 minutes/day or Fitbit wear was <4 days. Eligible participants will be randomized to 1 of 16 experimental conditions (4 factors, 2 levels each = <math>4^2=16</math>) and step count goals assigned.
 
Visit 2: Randomized participants will be called to review step goal; ineligible participants will be called to inform of study completion and will be asked to return the Fitbit via prepaid envelope.
 
Intervention: Participants will wear Fitbits daily for 12 weeks. Three nutrition recalls will be conducted via phone (weeks 1-2). A

---

---

safety check phone call (**Visit 3**) will take place during week 2 and another safety check and step count goal review phone call will take place during week 6 (**Visit 4**).

**Visit 5 (in-person):** After a 12-hour overnight fast at home, participants will attend the final study visit to undergo fasting laboratory evaluations, vitals, anthropometry, and exit interviews. Participants will return the Fitbit physical activity trackers.

---

Efficacy Evaluations	Change in minutes spent in MVPA (primary) and daily step count (secondary) from baseline to intervention week 12

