### **2.2 Secondary Objectives**

The secondary objectives are to:

- Determine the main and interactive effects of the four intervention components on:
  - Daily step count
  - body mass index Z-score
  - hemoglobin A1c
  - fasting insulin
  - fasting plasma glucose
  - fasting triglycerides, LDL, and HDL
  - AST, ALT
- Explore participant-reported intervention acceptability, including constructs of burden, perceived effectiveness, and impact on self-efficacy
- Assess baseline and intervention-related changes in intrinsic versus extrinsic motivation to pursue physical activity
- Assess the association between baseline delay discounting tendency and baseline and change in MVPA and step count
- Assess the correlation between Fitbit-measured physical activity and smartphone-measured physical activity

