**Table 1. Analysis plan**

Outcome	Analysis/statistical test
MVPA min/day: baseline vs 6 and 12 weeks ( primary outcome )	Mean/SD or median/IQR, ANOVA/ANCOVA
MVPA min/day: baseline vs 6 and 12 weeks	% of days with $\geq 60$ min/day, Fisher's exact test
MVPA min/day: average per week of intervention	% of days with $\geq 60$ min/day, Fisher's exact test
Steps/day: baseline (2 nd -week of run-in) versus 6 weeks and 12 weeks	Mean/SD or median/IQR, ANOVA/ANCOVA
Steps/day: baseline (2 nd -week of run-in) versus 6 weeks and 12 weeks	% of days with $\geq 10,000$ steps/day, Fisher's exact test
Steps/day: average per week of intervention	% of days with $\geq 10,000$ steps/day, Fisher's exact test
Body mass index Z-score	Mean/SD or median/IQR, ANOVA/ANCOVA
Hemoglobin A1c, insulin, glucose, triglycerides, LDL, HDL, AST, ALT	Mean/SD or median/IQR, ANOVA/ANCOVA
Hemoglobin A1c	% $<5.7\%$ , $5.7\text{-}6.4\%$ , $\geq 6.5\%$ , Fisher's exact test
Healthy Eating Index	Mean/SD or median/IQR, ANCOVA covariate, Pearson/Spearman correlation with demographic variables
Measure of delay discounting, k , derived from MCQ	Mean/SD or median/IQR, ANCOVA covariate (visit 1 measure), Pearson/Spearman correlation with demographic variables, paired t-test or Wilcoxon signed rank test to assess whether baseline and follow-up measures differ
Relative Autonomy Index (RAI) from BREQ-3	Mean/SD or median/IQR, ANCOVA covariate (visit 1 measure), Pearson/Spearman correlation with demographic variables, ANOVA/ANCOVA to assess change from visit 1 to 5 by experimental factor
PACE+: number of days with at least 60 minutes of activity per day in (a) past 7 days and (b) typical week	Mean/SD or median/IQR, Pearson/Spearman correlation with demographic variables and with number of days with MVPA $\geq 60$ minutes at baseline and week 12
Steps/week on smartphone activity tracker	Pearson/Spearman correlation with Fitbit-measured steps/week

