### 8.2 Data Collection and Management

Case report forms (CRF) in a REDCap database will be created by the study team for data capture. REDCap is a secure web-based data management software designed by Vanderbilt University investigators. Study data will be entered through intelligent REDCap forms that adapt to data content, and include built-in error checks to trap out-of-range or inconsistent entries into the central database.

The PI is responsible for the accuracy and completeness of data collection and management. The PI may designate qualified individual(s) to collect data and manage data. Only investigators and research staff that have completed appropriate IRB training and approval and are listed on the IRB approved protocol are eligible to collect and work on information from the study. Future studies that may use patients or data collected from this study must have separate approved IRB protocols and consent forms, if applicable. Data will be recorded onto the screening questionnaire after consent is documented. Original data will be recorded directly into CRFs by the study coordinator or a study investigator. Copies of laboratory, physical exam, anthropometric, and questionnaire responses will be received through the electronic medical record or through secured email. This information also will be recorded into CRFs in REDCap. The password to log into REDCap will be unique to each member of the study team.

**Fitbit Data:** Following enrollment and completion of the participant's Way to Health profile, study staff will help connect the participant's mobile device to the participant's Fitbit account and authorize W2H to access their data using OAuth. Participants will be asked to

download the free Fitbit app onto their smartphone to allow the Fitbit to sync at least once daily. Once the participant's account is authenticated to W2H, an hourly background job will query the vendor API for activity since the last data point that was downloaded. The daily Fitbit data will then be available to the study team on the secure, password-protected W2H platform and will be downloaded as a CSV file directly to the PI's institutional shared drive.

**Survey Data:** Participants will either complete surveys by hand or directly into REDCap. Study IDs will be used to link responses to participants. If used, responses on paper forms will be transferred via study staff to REDCap. Original paper forms will be stored in a secure file cabinet in the PI's office.

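### The exit interview and follow-up motivation questionnaire depend on attending in person, with nothing for withdrawals before 4 weeks, so both results may lean toward those who stay

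*Combined protocol and SAP*

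**What the plan says.** Two secondary objectives in section 2.2 are involved. One is to "Explore participant-reported intervention acceptability, including constructs of burden, perceived effectiveness, and impact on self-efficacy". The other is to "Assess baseline and intervention-related changes in intrinsic versus extrinsic motivation to pursue physical activity".

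For the first, the named instrument is the exit interview in section 5.1.8: "Semi-structured individual interviews will be conducted by study staff in a private setting at visit 5 to evaluate intervention acceptability". The Protocol Synopsis (Study Phases) describes Visit 5 as in person and after an overnight fast: "participants will attend the final study visit to undergo fasting laboratory evaluations, vitals, anthropometry, and exit interviews". For the second, the analysis plan table in section 6.5.3 specifies, for the RAI from the BREQ-3, "ANOVA/ANCOVA to assess change from visit 1 to 5 by experimental factor". The schedule of study procedures marks interview and surveys at Visits 1 and 5 only.

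Section 4.6.1 gives participants who withdraw the procedures listed for Visit 5 "as the early termination visit if at least 4 weeks have elapsed since the start of the 12-week intervention". It states nothing for earlier withdrawals. Section 3.1.4 adds a week 6 phone call that includes feedback on the intervention.

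Remote collection is already part of the trial. Section 8.2 states: "Participants will either complete surveys by hand or directly into REDCap". Dietary recalls of 30 minutes are done by phone (4.4.1), and re-consent at age 18 uses phone and REDCap (8.6.3).

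**The concern.** Someone who finds the texts, the goals or the incentive scheme burdensome may be more likely to leave. A participant who leaves before 4 weeks of intervention have elapsed is not offered the interview or the follow-up questionnaires. One who leaves later must make a clinic visit, with a fasting blood draw, to give either.

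This matters because section 6.5.2 compares interview themes by component level, and section 6.5.1 says the trial is meant to choose settings for an optimised intervention. If one level, for example twice-daily texts, led more people to leave early, its burden would be described mainly by those who tolerated it. The RAI change analysis would rest on the same selected group, and the missing-data section (6.5.4) gives no rule for missing interviews or RAI values. Neither measure needs clinic equipment.

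**Working it through.** **Who is reached, by route.**

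| Participant | Exit interview | Follow-up BREQ-3 |
|---|---|---|
| Completes and attends Visit 5 | Yes (4.5.1, 5.1.8) | Intended (schedule of procedures, analysis plan table), but not listed in 4.5.1 |
| Withdraws at 4 weeks or later and attends | Yes (4.6.1) | Unclear: 4.6.1 takes over the Visit 5 procedures, and 4.5.1 lists no questionnaires |
| Withdraws at 4 weeks or later, does not attend | No stated route | No stated route |
| Withdraws before 4 weeks | No | No |

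The second column shows an inconsistency. The schedule of procedures and the RAI analysis need questionnaires at Visit 5, but the Visit 5 list in section 4.5.1 omits them. The passages need to be reconciled.

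**How many could be missed.** Inputs from section 6.6: 75 recruited, 64 evaluable, 15% dropout.

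- The plan's own figure: 64 / 0.85 = 75.3, against 75 stated. In reverse, 75 × 0.85 = 63.75, or about 64. The recruitment figure is reproduced.
- Expected leavers: 75 − 64 = 11.
- Lower case. Assume withdrawals are even over the 12 weeks and every later leaver attends the early termination visit. Then 4/12 of 11 = 3.7, so about 4 of 75 are missed.
- Upper case. Assume no leaver attends. Then about 11 of 75 are missed.

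Both cases treat all 75 as randomised. The documents do not say whether the 15% includes people withdrawn after the run-in. Any such people never received the intervention and have no view of it to miss.

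**Illustration only.** Suppose a yes/no acceptability rate existed, with 80% of the 64 completers favourable and a share q of the 11 leavers favourable, q from 0 to 0.3. These inputs are assumed. The rate in all 75 is (51.2 + 11q) / 75, which is 68.3% at q = 0 and 72.7% at q = 0.3.

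- None of the 11 reached: observed 80%, a difference of 11.7 to 7.3 points.
- 7 of the 11 reached: observed (51.2 + 7q) / 71, which is 72.1% at q = 0 and 75.1% at q = 0.3, a difference of 3.8 to 2.4 points.
- Leavers and completers rate alike: the difference is 0 in both cases.

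**RAI precision.** With variance proportional to 1/n, going from 64 to 75 gives 64/75 = 0.853, a reduction of at most about 15%. Going from 71 to 75 gives 71/75 = 0.947, about 5%. Both assume that an early leaver's RAI change is as informative as a completer's.

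**The case against.** A reader might infer that those who leave early are simply not asked. The documents do not support that. Section 4.6.1 gives the exit interview to people who withdraw once 4 weeks have elapsed, and section 8.7.2 pays $50 plus $20 travel for completing Visit 5. The week 6 call also seeks feedback by phone, so the exit interview is not the only route. This stands in part: the call comes too late for the earliest leavers, the Visit 4 procedure list (4.4.3) does not mention feedback, and section 6.5.2 describes analysis of the exit-interview transcripts only.

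A reader might also infer that acceptability is overstated by some 7 to 12 points. That is not supported either. Acceptability is explored through semi-structured interviews and coded into themes. The documents contain no acceptability scale, cut-off or planned rate, and they give no timing of dropout or reasons for it. That range also needs no leaver to be reached and all 75 to be randomised.

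Two practical objections stand. An RAI score from someone who left in week 1 or 2 reflects little exposure and a different time point, so it may add less than its count suggests. And section 5.1.8 asks for a private setting with audio recording, which a call to a 13- to 17-year-old at home may not provide.

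**Conclusion.** The point holds as a gap in coverage, not as a demonstrated bias. By design, randomised participants who withdraw before 4 weeks of intervention get neither the exit interview nor the follow-up questionnaire, and no remote route is stated for later leavers who do not attend. Component-level acceptability themes and the RAI change analysis may therefore be tilted toward those who stay. That direction is plausible but cannot be shown from the documents.

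The number missed is about 4 of 75 if withdrawal is even over 12 weeks and later leavers all attend, and up to about 11 if none attend and all 75 are randomised. The bias could be zero if people leave for unrelated reasons. This is a cheap improvement to secondary objectives and does not affect the primary MVPA analysis.

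**What to change.** - In sections 5.1.8, 4.5.1 and 4.6.1, offer the exit interview by phone and the Visit 5 questionnaires by REDCap link to every randomised participant who withdraws at any time, or misses Visit 5, and agrees to be contacted.
- List the questionnaires in section 4.5.1, so that it agrees with the schedule of procedures and the RAI analysis, and so that section 4.6.1 carries them over.
- Report by factor level how many leavers were reached. A percentage with all randomised participants as denominator does not suit a thematic analysis.
- Flag RAI values from early withdrawals by time since randomisation, and add a sensitivity analysis that excludes them.

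Cost: at most about 11 calls of up to 30 minutes (11 × 0.5 = 5.5 hours), plus REDCap links. Some leavers will decline. Interview mode and timing will differ between leavers and completers, which should be stated when themes are compared. Staff should confirm privacy at the start of each call.

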### 5.1.9 Personal smartphone activity tracker data

Once weekly during the 12-week intervention, participants will be asked (via text message) to send in a screenshot of their smartphone's activity tracker's step count measurement for the week. Step counts will be abstracted via study staff and entered into a secure REDCap.

**Figure 4.** Example of smartphone activity tracker data summary

